10.5. Baseline Assessments

The following assessments must be completed prior to the index procedure. The eCRFs identify the specific data points to be collected.

- Confirmation of eligibility criteria
- NYHA classification
- Laboratory tests
 - Cardiac enzymes (CK [creatinine kinase] or troponin is required, CK-MB [creatinine kinase myoglobin band] or troponin if CK is elevated)
 - Plasma-free hemoglobin
 - Complete blood count (CBC) with platelets
 - Serum creatinine

10.6. Pre-procedure/Procedural Medications

Subjects should be treated with heparin during the procedure. Activated clotting time (ACT) should be measured as standard of care with a recommended target of >250 and <400 seconds for the duration of the procedure.

10.7. Index Procedure

The preparation of the subject for the percutaneous procedure will be performed following standard techniques.

10.7.1. Vortex System Procedure

The investigational device will be delivered on a guidewire through a Vortex introducer sheath catheter from the femoral artery access site to the aorta and positioned across the aortic valve. During the transcatheter approach, the subject is under conscious sedation.

Please refer to the Vortex IFU and investigator training materials (see Section 15.4.1) for detailed instructions on procedural steps.

Note 1: All Vortex procedures will be performed with the support/presence of trained BSC personnel.

Note 2: Plasma-free hemoglobin may be collected during the index procedure per the standard of care.

The following information will be collected during the procedure. Additional data to be collected will be outlined in the eCRF.

- Date of procedure
- Time of first vascular puncture (femoral) and vascular closure (skin-to-skin time)
- Vortex System insertion and removal time
- Additional information regarding use of the Vortex System
 - Descriptive information on Vortex System insertion procedure
 - Descriptive information on Vortex System positioning and retrieval
 - Descriptive information on the impact of the Vortex System on cardiac anatomy and physiology
 - Impact of Vortex System usage on HR-PCI procedure success
- ECG changes (per standard of care)
- Adverse event assessment; see Section 18
- Device deficiencies assessment

10.7.2. Intraprocedural Cardiac Imaging

Subjects will undergo heart catheterization with radiographic imaging as per standard of care. Imaging may include fluoroscopy, ventriculography, and/or sonography before and after placement of the Vortex System to assess the left ventricle and verify freedom from coronary interference. Minimization of contrast media injected into subjects with compromised renal function is recommended.

Deidentified copies of the imaging assessments should be provided to Boston Scientific.

10.7.3. Intraprocedural Hemodynamic Measurements

Intraprocedural hemodynamic assessment is primarily based on TTE (or intracardiac echocardiography³³ as per standard of care) and catheter-based pulmonary artery measurements. Cardiac output (CO), pulmonary artery (PA) pressure, pulmonary capillary wedge pressure (PCWP), central venous pressure (CVP), mean arterial pressure (MAP), and right atrial pressure (RAP) should be measured before and after the pump is placed and switched on via the pulmonary artery catheter and also when the pump is switched off and

removed (post-procedure). Left ventricular pressure may be measured via the pigtail catheter.

10.8. *Post-procedure (≤ 72 Hours)/Prior to Hospital Discharge*

Within 72 hours post procedure or before discharge (whichever comes first), the following assessments must be performed.

- 12-lead ECG
- Laboratory tests
 - Cardiac enzymes (CK or troponin required, CK-MB or troponin if CK is elevated) must be collected once per standard of care within 6–24 hours post-procedure; if readings are abnormal, a second collection per standard of care is required.
 - Plasma-free hemoglobin must be collected ≥ 6 hours post procedure (before discharge)
- NYHA classification
- Anticoagulation therapy and other cardiovascular medications
- Adverse event assessment (see Section 18)
- Device deficiencies assessment

10.9. *Study Completion*

All subjects will be evaluated through 72 hours or hospital discharge, whichever comes first. A subject's participation in the study will be considered complete after 72 hours or hospital discharge (whichever comes first).

10.10. *Source Documents*

It is preferable that original source documents, when available, are maintained at the investigative center. In lieu of original source documents, certified copies are required to be maintained. A certified copy is a copy (irrespective of the type of media used) of the original record that has been verified (i.e., by a dated signature or by generation through a validated process) to have the same information, including data that describe the context, content, and structure, as the original. Source documentation includes but is not limited to those items noted in **Table 10.10-1**. Source documentation provided to the Sponsor for assessment/adjudication will be deidentified per local law and regulations.

Table 10.10-1: Source Documentation Requirements

Requirement	Disposition
Printed, optical, or electronic document containing source data. Examples may include but are not limited to hospital records, laboratory notes, device accountability records, photographic negatives, radiographs, records kept at the investigation center, at the laboratories and at the medico-technical departments involved in the clinical investigation.	Retain at center.

Note: Please see Table 24.2-1 for definitions of “source data” and “source document.”

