d: 12-lead ECG; baseline ECG should be done within 30 days prior to the index procedure; post-procedure timing is per standard of care for HR-PCI.

e: Laboratory tests at baseline include CBC with platelets, serum creatinine, plasma-free hemoglobin, and cardiac enzymes. Post-procedure, cardiac enzymes (CK or troponin is required, CK-MB or troponin if CK is elevated) must be collected once per standard of care within 6–24 hours; if readings are abnormal, a second collection per standard of care is required. Plasma-free hemoglobin must be collected pre-discharge (≥ 6 hours post procedure). Plasma-free hemoglobin may be collected during the index procedure per the standard of care.

f: Minimum required iliofemoral diameter is > 5.5 mm; any assessment technique to determine diameter and tortuosity is permitted; assessment must be done within 365 days prior to the index procedure.

g: TTE assessment should be done within 180 days prior to the index procedure.

h: Deidentified copies of the imaging assessments should be provided to Boston Scientific.

i: Coronary angiogram should be done within 365 days prior to the index procedure per standard of care for HR-PCI.

j: Information on device deficiencies for the test device will be monitored and reported to Boston Scientific.

k: The adverse event assessment includes AE, SAE, ADE, SADE, USADE, and IMR events, which will be collected from the time of enrollment through 72 hours post-procedure or hospital discharge, whichever comes first, in all subjects. Please refer to Section 18.1 for reportable events, including a list of IMR events, and to **Table 24.2-1** for definitions of these events, which specify data required for IMR adjudication.

Abbreviations: AE=adverse event; ADE=adverse device effect; CBC=complete blood count; CCS=Canadian Cardiovascular Society; CK=creatinine kinase; CK-MB=creatinine kinase myoglobin band; ECG=electrocardiogram; HR-PCI=high risk percutaneous coronary intervention; IMR=independent medical

Table 10.1-1: Data Collection Schedule

Assessment	Baseline	Index Procedure	≤72 Hours / Discharge ^a
------------	----------	-----------------	------------------------------------

reviewer; SADE=serious adverse device effect; SAE=serious adverse event; USADE=unanticipated serious adverse device effect

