	
The term myocardial injury should be used when there is evidence of elevated cardiac troponin values (cTn) with at least one value above the 99th percentile upper reference limit (URL). The myocardial injury is considered acute if there is a rise and/or fall of cTn values.
 
 • Criteria for Acute Myocardial Infarction (types 1, 2 and 3 MI) The term acute myocardial infarction should be used when there is acute myocardial injury with clinical evidence of acute myocardial ischaemia and with detection of a rise and/or fall of cTn values with at least one value above the 99th percentile URL and at least one of the following: 
 ○ Symptoms of myocardial ischaemia; ○ New ischaemic electrocardiogram (ECG) changes; ○ Development of pathological Q waves; ○ Imaging evidence of new loss of viable myocardium or new regional wall motion abnormality in a pattern consistent with an ischaemic aetiology; ○ Identification of a coronary thrombus by angiography or autopsy (not for type 2 or 3 MIs). 
Type 1 MI: Post-mortem demonstration of acute athero-thrombosis in the artery supplying the infarcted myocardium meets criteria for type 1 MI.
 
Type 2 MI: Evidence of an imbalance between myocardial oxygen supply and demand unrelated to acute athero-thrombosis meets criteria for type 2 MI.
 
Type 3 MI: Cardiac death in patients with symptoms suggestive of myocardial ischaemia and presumed new ischaemic ECG changes before cTn values become available or abnormal meets criteria for type 3 MI.
 • Criteria for Coronary Procedure-Related Myocardial Infarction (types 4 and 5 MI) Percutaneous coronary intervention (PCI) related MI is termed type 4a MI. Coronary artery bypass grafting (CABG) related MI is termed type 5 MI. Coronary procedure-related MI \leq 48 hours after the index procedure is arbitrarily defined by an elevation of cTn values $>$ 5 times for type 4a MI and $>$ 10 times for type 5 MI of the 99th percentile URL in patients with normal baseline values. Patients with elevated pre-procedural cTn values, in whom the pre-procedural cTn level are stable (\leq 20% variation) or falling, must meet the criteria for a $>$ 5- or $>$ 10-fold increase and manifest a change from the baseline value of $>$ 20%. In addition, with at least one of the following: 
 ○ New ischaemic ECG changes (this criterion is related to type 4a MI only); ○ Development of new pathological Q waves; ○ Imaging evidence of loss of viable myocardium that is presumed to be new and, in a pattern, consistent with an ischaemic aetiology; ○ Angiographic findings consistent with a procedural flow-limiting complication such as coronary dissection, occlusion of a major epicardial artery or graft, side-branch occlusion-thrombus, disruption of collateral flow or distal embolization. 
Type 4a MI or Type 5 MI: Isolated development of new pathological Q waves meets the type 4a MI or type 5 MI criteria with either revascularization procedure if cTn values are elevated and rising but less than the pre-specified thresholds for PCI and CABG.

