
Table 24.2-1: Definitions

Term	Definition								
	
Type 4b MI and Type 4c MI: Other types of 4 MI include type 4b MI stent thrombosis and type 4c MI criteria.
 
Type 4a MI and Type 4b MI: Post-mortem demonstration of a procedure-related thrombus meets the type 4a MI criteria or type 4b MI criteria if associated with a stent.
 
 • Criteria for Prior or Silent/Unrecognized Myocardial Infarction Any one of the following criteria meets the diagnosis for prior or silent/unrecognized MI: 
 ○ Abnormal Q waves with or without symptoms in the absence of nonischaemic causes ○ Imaging evidence of loss of viable myocardium in a pattern consistent with ischaemic aetiology ○ Patho-anatomical findings of a prior MI 								
NEUROLOGICAL EVENT	Any central, new neurological deficit, whether temporary or permanent and whether focal or global, that occurs after the subject emerges from anesthesia								

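### Centers may measure CK/CK-MB instead of troponin, but types 1/2 and 4a/5 MI in survivors are defined only through troponin, so status for these types cannot be determined in some survivors

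*Protocol*

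**What the plan says.** **What is collected.** Protocol 10.8 sets the post-procedure cardiac enzymes as "CK or troponin required, CK-MB or troponin if CK is elevated". Footnote e of Table 10.1-1 says the same: "CK or troponin is required, CK-MB or troponin if CK is elevated". Protocol 10.5 applies the choice at baseline: "CK [creatinine kinase] or troponin is required". After the procedure there is one collection at 6–24 hours and a second only if the first is abnormal. The text does not say which assay the second must use.

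**What defines the event.** Protocol Section 11 refers to Table 24.2-1 for event definitions.
- Types 1 and 2 need acute myocardial injury "with detection of a rise and/or fall of cTn values with at least one value above the 99th percentile URL", plus at least one supporting finding (symptoms, ECG, Q waves, imaging or coronary thrombus, the last not for type 2).
- Procedure-related MI "is arbitrarily defined by an elevation of cTn values" above 5 times (type 4a) or 10 times (type 5) the 99th percentile upper reference limit (URL), with a condition on the baseline cTn. The definition continues "In addition, with at least one of the following" and lists ECG, Q-wave, imaging and angiographic findings.
- Isolated new Q waves qualify as 4a or 5 only "if cTn values are elevated and rising but less than the pre-specified thresholds".
- The MI row contains no CK or CK-MB criterion.

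**How it is reported.** MI is an additional measurement (Protocol 6.3, SAP 3.2) and is not among the events sent to the Independent Medical Reviewer. SAP 3.2.1 reports a numerator, a denominator and a proportion. SAP 7.4.3 keeps every subject of the analysis set in the denominator and treats all as having sufficient follow-up. SAP 7.3 leaves the handling of missing data open.

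**The concern.** The collection rule and the event definition do not match. A fully compliant center can hold CK and CK-MB values for a subject and still lack the one biomarker that the definition uses. If that subject also has, say, new ischemic ECG changes, the protocol offers no way to call the event either way for types 1/2 or 4a/5.

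No later step catches this. MI is not independently adjudicated, the SAP has no category for an undeterminable status, and the subject stays in the denominator. Whether such a subject appears as an event, a non-event or missing is not fixed in advance. In a first-human-use study whose objective includes safety, the descriptive count is the whole result for MI, so a reader needs to know whether 0/n means that MI was excluded or that it could not be judged. Troponin that was never drawn may not be recoverable afterwards.

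**Working it through.** The plan gives no figure for MI, and its maximum of 10 subjects is set arbitrarily, so there is nothing to reproduce. The check sets the passages side by side and then bounds the effect.

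**Step 1. Which assay sets comply without troponin?** Under 10.5, 10.8 and footnote e: CK alone if it is not elevated, and CK with CK-MB whether or not CK is elevated. CK alone when elevated does not comply. Compliance without troponin is therefore possible at both time points.

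**Step 2. Status for types 1/2 and 4a/5 in a survivor.** The rule is cTn criterion AND supporting criterion.

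| cTn criterion | Supporting: met | Supporting: evaluated, none | Supporting: none met, one or more not evaluated |
|---|---|---|---|
| Met | MI | not MI | undetermined |
| Not met | not MI | not MI | not MI |
| No troponin | **undetermined** | not MI | **undetermined** |

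The bold cells arise from the assay choice. The undetermined cell in the top row does not, and requiring troponin would not remove it.

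**Step 3. CK at baseline, troponin only afterwards.** Given a supporting finding met or not evaluated, status is also uncertain in three situations:
- A single post-procedure cTn lies above the 99th percentile URL. Types 1/2 need a rise and/or fall, which one value cannot show.
- cTn exceeds the 4a/5 threshold. Whether baseline cTn was normal, or elevated but stable or falling with a change of more than 20%, cannot be checked.
- New Q waves appear. The isolated Q-wave route needs a rising cTn, and there is no baseline value to compare with.

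**Step 4. Can a finding be unevaluated within the plan?** Table 10.1-1 requires a post-procedure 12-lead ECG, and transthoracic echocardiography and a coronary angiogram at the index procedure. It schedules no imaging in the 72-hour/discharge column, and footnote d leaves the ECG timing to standard of care. So later imaging is the main gap. The met cell needs no gap at all.

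**Step 5. Routes not affected.** These are type 3 and the post-mortem routes, prior or silent MI, and types 4b/4c, which are named ("Other types of 4 MI include") without a cTn threshold.

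**Step 6. Size.** Let n be the subjects in the analysis set, x the MIs confirmed, and m the survivors undetermined for these types. The data then allow any proportion from x/n to (x + m)/n. The documents do not give m, so it is an assumption with range 0 to n − x.

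| n | x | m (assumed) | Possible MI proportion |
|---|---|---|---|
| 10 | 0 | 0 | 0/10 = 0% |
| 10 | 0 | 1 | 0/10 to 1/10 = 0–10% |
| 10 | 0 | 2 | 0/10 to 2/10 = 0–20% |
| 10 | 0 | 3 | 0/10 to 3/10 = 0–30% |
| 10 | 1 | 1 | 1/10 to 2/10 = 10–20% |
| 5 | 0 | 1 | 0/5 to 1/5 = 0–20% |

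m cannot exceed k, the number without usable troponin. If k = 5 of 10 (assumed), the upper bound is 10% when one of the five has a finding met or not evaluated, 30% when three do, and 50% only when all five do.

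For scale, the exact (Clopper-Pearson) 95% interval is 0–30.8% at 0/10, 0.3–44.5% at 1/10 and 6.7–65.2% at 3/10.

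**The case against.** The strongest reply is that nothing shows the problem will occur. The documents do not say that any center would use CK alone, both m and k are assumed, and at 0/10 sampling error already allows 30.8%. MI has no hypothesis and lies outside the primary endpoint. All adverse events are reportable, abnormal laboratory findings included. SAP 5.6 foresees subject listings, and ten subjects can be reviewed one by one.

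Much of this stands, and it limits the weight of the point. It does not remove it. Adverse event reporting would bring the subject to notice but would not supply the missing criterion. The SAP 5.6 listings are optional, and an investigator's judgement without troponin would not follow the protocol's own definition.

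A second objection concerns the word unassessed. If any finding without later imaging counts as unassessed, nearly every CK-only survivor becomes undetermined. If only positive evidence counts, missing imaging means a non-event. This is fair: the term needs a definition before such subjects are counted.

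Three stronger readings are tempting and are not supported:
- That MI status as a whole is undeterminable. Prior or silent MI, types 4b/4c, type 3 and the post-mortem routes do not depend on a stated cTn threshold.
- That every survivor without troponin is undeterminable. One who was evaluated and has no supporting finding is a non-event.
- That the reported MI proportion will be too low. The documents show only that it could be unsupported, by an unknown number of subjects.

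**Conclusion.** The mismatch is real and internal to the protocol. In survivors without troponin, status for types 1/2 and 4a/5 MI is undetermined when a supporting finding is present, or when none is present but one was not evaluated. Some survivors with troponin only after the procedure are affected too. The planned MI table would not show any of them.

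Each affected subject widens the possible MI proportion by 10 percentage points at n = 10. How many there will be is an assumption, from zero upward. The consequence is confined to a descriptive safety measurement; Technical Success and Clinical Success are untouched. It should be corrected because the remedy is small and a missing assay may not be recoverable later.

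**What to change.** **Protocol.** Reconcile the passages in one of two ways:
1. In 10.5, 10.8 and footnote e of Table 10.1-1, require cardiac troponin at the existing baseline draw and the existing post-procedure draw, including the conditional second collection when the first is abnormal. CK/CK-MB become optional.
2. Keep the assay choice, and have the sponsor state in Table 24.2-1 an MI criterion for each permitted assay.

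**SAP 3.2.1 and 7.4.3.** Keep the full ITT and per-protocol denominators. Beside the MI proportion, report and list the subjects whose type 1/2 or 4a/5 status could not be determined. Define unassessed, for example as no post-procedure ECG, or a clinically indicated imaging or angiographic evaluation not done; the mere absence of unscheduled imaging would not count. Subjects evaluated and found to have no supporting finding remain non-events.

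**Cost and limits.** Option 1 adds a troponin assay on the same draw at centers that use CK. Option 2 avoids that, but the sponsor must choose and justify the criteria. Either needs a protocol amendment with ethics committee and Swedish Medical Products Agency approval (Protocol 15.3), plus one count and one listing in the output. Option 1 does not close everything: when pre-procedural cTn is elevated, a single baseline value may not show whether it was stable or falling. Those subjects belong in the undetermined count.

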10.11. Local Laboratory/Vendor Documentation

This study requires local laboratory results. Appropriate certifications and documentation records are required to be maintained at the center.

11. Statistical Considerations

Event definitions can be found in **Table 24.2-1**.

11.1. Endpoints

11.1.1. Primary Endpoint

The primary endpoint consists of Technical Success and Clinical Success. Technical Success is defined as successful delivery of the device to the correct anatomical position and successful operation and removal of the Vortex System. Clinical Success is defined as no conversion to open heart surgery or in-hospital mortality.

11.1.1.1. Hypotheses

There is no formal statistical hypothesis in this observational feasibility study.

11.1.1.2. Sample Size

This is a prospective non-randomized feasibility study with no formal pre-specified hypothesis and therefore sample size estimates are not applicable. To support the stated objective of this feasibility study, while also limiting the potential exposure to risk of study subjects, the study sample size has been arbitrarily set at a maximum of 10 subjects enrolled.

11.1.1.3. Statistical Methods

Descriptive statistics will be used for baseline, procedure, and follow-up data collected during the study. See Section 11.2.1 for a discussion of analysis sets.

11.1.2. Additional Measurements

Additional measurements are listed in Section 6.3. There are no statistical hypotheses for the additional measurements.

11.2. General Statistical Methods

All statistical analyses will be performed using the SAS System software, version 9.2 or later (Copyright© 2000 SAS Institute Inc., [name], USA. All rights reserved).

All statistical analyses will be conducted according to applicable Standard Operating Procedures, Work Instructions, and the study-specific statistical analysis plan.

11.2.1. Analysis Sets

The primary endpoint and additional measurements will be analyzed on an intention-to-treat (ITT) basis and a per-protocol basis. Analysis sets are listed below. Subjects are considered enrolled in the study as soon as an attempt is made to insert any part of the Vortex System into the subject's femoral artery.

- ITT: This population includes all subjects who sign an ICF and are enrolled in the study, whether or not a study device is successfully inserted and used.
- Per-protocol: This population includes all ITT subjects in whom the device is successfully advanced across the aortic valve into the left ventricular outflow tract and turned on.

